11. DATA MANAGEMENT

Each site is responsible for accurate, complete, and timely collection/recording of data using the CRF (or EDC system) provided. Data will be stored in a validated and secure database for analysis. ConforMIS will periodically review all data, and specifically adverse event data to determine interim revision rates, frequency of serious adverse device effects and subject outcomes. If missing data fields or incorrect data are identified, the site may be contacted to provide the missing/correct data. ConforMIS or a designee will provide Case Report Forms (paper and/or electronic) to the study sites, along with access to the EDC system.

12. MONITORING

ConforMIS or designee will monitor clinical sites to review source data, study conduct, and compliance to the protocol. Each site will be monitored shortly after beginning enrollment to ensure early identification and resolution of any issues. After the initial monitoring visit, the site will be monitored at a frequency determined by ConforMIS or designee based on a variety of variables including, but not limited to, the rate of enrollment, the number of issues identified that require follow-up, changes in site personnel, etc.

13. STATISTICAL METHODS

All statistical processing will be performed using SAS® Version 9.2 or later unless otherwise stated. Efficacy analyses performed using the intent-to-treat (ITT) population will be considered primary. Safety analyses will be performed on the safety population.

No imputations will be made for missing observations. Continuous variables will be summarized with sample size, mean, standard deviation, median, minimum, maximum, and 95% confidence intervals, as appropriate. Categorical variables will be summarized with frequency counts, percentages, and 95% confidence intervals, as appropriate.

Populations

The safety population will be comprised of all subjects for whom the procedure is initiated.

The ITT population will be comprised of all subjects for whom the procedure is completed.

Demographic and Baseline Evaluations

Demographic variables (age, gender, ethnicity, and race) will be recorded in the eCRF and summarized using descriptive statistics.

Efficacy Analysis

Primary Efficacy Analysis

There is one primary endpoint, change from baseline to 1-Year in KSS. Hypothesis testing of the primary endpoints will be conducted for the ITT population, and will be analyzed with paired t-test.

Secondary Efficacy Analyses

Secondary endpoints will be analyzed for the ITT population. Details of statistical testing for each endpoint will be further discussed in the Statistical Analysis Plan.

1. Change from baseline in KSS at years 2, 5 and 10 post-implantation
2. Change from baseline in KOOS at years 1, 2, 5 and 10 post-implantation
3. Post-operative limb alignment if long leg x-rays available
4. Length of hospital stay in hours (admission to discharge)
5. Blood loss during surgery
6. Transfusion rate

Supportive Efficacy Endpoints

1. Revision rates post-implantation
2. Radiographic loosening, radiolucencies
3. Length of procedure: Skin to Skin

Safety Analysis

All adverse events (AEs) occurring during the study will be recorded and classified. For the safety population, all reported AEs will be summarized by the number of subjects reporting AEs, severity, relationship to procedure, relationship to device, and seriousness. For summaries of AEs by relationship or severity, each subject will be counted only once using the event with the greatest relationship or highest severity.

In addition to overall AE summaries, AEs will be summarized for the following study periods:

- Day of procedure to 6 months post procedure
- Annual summaries (1 Year, 2 Year, etc.) from day of procedure

Serious adverse events (SAEs) will be summarized by group, severity, relationship to procedure, and relationship to device. SAEs will also be listed by subject.

All information pertaining to AEs noted during the study will be listed by subject.

Sample Size Determination

The sample size for this study was not based on a power analysis. However, a sample size of up to 50 subjects is considered to provide adequate estimation of the study endpoints.

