5. STUDY ENDPOINTS

5.1. Primary Endpoint

The study primary endpoint is pain and function at 1 Year after implantation, as measured by:

1. Knee Society Clinical Rating Score
 - 1.1. Objective Knee Score
 - 1.2. Function Score
 - 1.3. Satisfaction Score
 - 1.4. Expectation Score

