6. INCLUSION AND EXCLUSION CRITERIA

6.1. Inclusion Criteria

1. Clinical condition included in the approved Indications For Use for the iTotal® CR

2. Osteoarthritis, as confirmed by the investigator's assessment of disease status at screening visit that warrants a TKR procedure. Disease status is assessed by Clinical and Radiographic assessment.
3. Willingness to participate in the clinical study, to give informed consent, and to attend all follow-up visits
4. > 18 years of age

6.2. **Exclusion Criteria**

1. Simultaneous bilateral procedure required
2. BMI > 40
3. Active malignancy (defined as a history of any invasive malignancy – except non-melanoma skin cancer), unless patient has been treated with curative intent and there have been no clinical signs or symptoms of the malignancy for at least 5 years
4. Poorly controlled diabetes
5. Neuromuscular conditions which prevent patient from participating in study activities
6. Active local or systemic infection
7. Immunocompromised
8. Fibromyalgia or other general body pain related condition
9. Rheumatoid arthritis or other forms of inflammatory joint disease
10. Loss of bone or musculature, osteonecrosis, neuromuscular or vascular compromise in the area of the joint to be operated on, to an extent that the procedure is unjustified
11. Diagnosed with or receiving treatment for Osteoporosis
12. Other physical disability affecting the hips, spine, or contralateral knee
13. Severe instability due to advanced loss of osteochondral structure
14. Prior arthroplasty of the affected knee, including High Tibial Osteotomy (HTO)
15. Compromised PCL or collateral ligament
16. Severe fixed valgus or varus deformity of >15°
17. Extensor lag > 15°
18. Fixed flexion contracture ≥ 15°
19. Unwilling or unable to comply with study requirements
20. Participation in another clinical study which would confound results
21. Allergy to any of the implant materials

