9.2. Surgery Visit (Day 0)

The Investigator surgically implants the iTotal® CR and iPoly XE inserts in compliance with the ConforMIS surgical training and iTotal® CR Instructions for Use.

The site completes the following Case Report Forms:

- SURGICAL SUMMARY
- DISCHARGE SUMMARY
- PAIN MEDICATIONS (update if changes have occurred)
- CONCOMITANT MEDICATIONS (update if changes have occurred)
- ADVERSE EVENTS / SERIOUS ADVERSE EVENTS (if any occur during surgery through discharge from hospital)

X-rays: None

9.3. 12-Week Follow-up Visit (± 2 weeks)

At the 12-week follow-up visit, the Investigator or study staff performs a post-operative knee assessment and identifies any adverse events that have occurred since the subject was discharged from the hospital.

The site completes the following Case Report Forms:

- FOLLOW-UP FORM
- KNEE SOCIETY SCORE (Surgeon portion)
- PAIN MEDICATIONS (update if changes have occurred)
- CONCOMITANT MEDICATIONS (update if changes have occurred)
- ADVERSE EVENTS (if any)
 - REVISION FORM (if necessary)

The subject completes the following questionnaires to assess post-operative pain and function:

- THE KNEE INJURY AND OSTEOARTHRITIS OUTCOME SCORE (KOOS)
- KNEE SOCIETY SCORE (Subject portion)

X-rays:

- 3 views – AP, lateral, sunrise or Merchant

- Three-foot standing x-ray (full length, full weight-bearing film): AP view

9.4. 6-Month follow-up visit (\pm 3 weeks)

At the 6-month follow-up visit, the Investigator or study staff performs knee assessments and identifies any adverse events that have occurred since the last visit.

The site completes the following Case Report Forms:

- FOLLOW-UP FORM
- KNEE SOCIETY SCORE (Surgeon portion)
- PAIN MEDICATIONS (update if changes have occurred)
- CONCOMITANT MEDICATIONS (update if changes have occurred)
- ADVERSE EVENTS (if any)
 - REVISION FORM (if necessary)

The subject completes the following questionnaires to assess post-operative pain and function:

- THE KNEE INJURY AND OSTEOARTHRITIS OUTCOME SCORE (KOOS)
- KNEE SOCIETY SCORE (Subject portion)

X-rays: None

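### The primary 1-year KSS analysis is a completers' paired t-test under an ITT label and leaves the mandated 12-week and 6-month scores unused; a repeated-measures model is a cheap improvement.

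*Combined protocol and SAP*

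**What the plan says.** Section 5.1 sets the goal: "The study primary endpoint is pain and function at 1 Year after implantation", measured by the KSS, with four component scores listed. Section 13 makes it operational:

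- Endpoint: "There is one primary endpoint, change from baseline to 1-Year in KSS".
- Test: it "will be analyzed with paired t-test", in the ITT population, which is declared primary for efficacy.
- Analysis set: "The ITT population will be comprised of all subjects for whom the procedure is completed".
- Missing data: "No imputations will be made for missing observations". No sensitivity analysis is named.

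Sections 9.3 and 9.4 collect the subject and surgeon portions of the KSS at 12 weeks and 6 months, and Appendix A marks both as mandated. Section 9.8 asks sites to attempt a KSS at early termination but gives no rule for using it. The only pointer to a further SAP concerns statistical testing and stands under the secondary analyses.

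**The concern.** The analysis set and the test do not match. A subject can be in the ITT population without a 1-year KSS, but cannot contribute to a paired t-test of the 1-year change. The documents do not state this exclusion in words; it follows from the named test and the no-imputation rule. The label says ITT and the estimate is for completers.

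The completers' mean is unbiased only if missing year 1 is unrelated to the 1-year change. The 12-week and 6-month scores could partly correct for a relation of that kind, and the t-test cannot use them. The study has one device group and no power calculation; Section 13 says that "a sample size of up to 50 subjects is considered to provide adequate estimation of the study endpoints". The mean change and its interval are therefore the main product, and an error in the estimate matters even where the test result would not change.

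**Working it through.** The plan states no SD, expected change, dropout rate or power, so there is no figure of its own to reproduce. What follows is illustrative.

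**Inputs from the documents.** Endpoint, test, analysis set and missing-data rule (Section 13); KSS visits (Sections 9.3-9.5, Appendix A); n = 50 (Section 13; Section 3 allows 50 to 60).

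**Assumptions.** Year-1 missingness of 5%, 10% or 20%. KSS changes at 12 weeks, 6 months and 1 year with unit SD; correlation between adjacent visits 0.6 or 0.8, and between 12 weeks and 1 year 0.5 or 0.7. The log-odds of missing year 1 rise by 0.5 or 1 per SD of poorer change. 20,000 simulated trials per scenario.

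**Step 1: precision.** With m subjects in the t-test, the 95% half-width in SD units is t(0.975, m-1)/√m.

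- n = 50: m = 50, 45, 40 at 0%, 10%, 20% missing gives 0.284, 0.300, 0.320.
- n = 60: m = 60, 54, 48 gives 0.258, 0.273, 0.290.

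The loss of precision is modest.

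**Step 2: bias of the t-test when missingness follows the 6-month change** (lower / higher correlation):

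| Missing | Slope | Bias (SD) | Coverage of nominal 95% CI |
|---|---|---|---|
| 5% | 0.5 | 0.014 / 0.019 | 0.947 / 0.948 |
| 10% | 0.5 | 0.031 / 0.040 | 0.945 / 0.940 |
| 20% | 0.5 | 0.058 / 0.076 | 0.934 / 0.924 |
| 5% | 1 | 0.028 / 0.036 | 0.946 / 0.943 |
| 10% | 1 | 0.052 / 0.071 | 0.936 / 0.923 |
| 20% | 1 | 0.105 / 0.139 | 0.900 / 0.857 |

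Hand check: bias = fraction missing × (completers' mean − mean of those missing). The implied gap is 0.031/0.10 = 0.31 SD in the mildest 10% case and 0.139/0.20 = 0.70 SD in the worst 20% case. Against the half-width, these biases are 0.031/0.300 = 0.10 and 0.139/0.320 = 0.43.

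**Step 3: what a likelihood model recovers.** These runs modelled the three post-operative changes by maximum likelihood with unstructured covariance.

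- 6-month score present: absolute bias at most 0.002 SD.
- Half of those missing year 1 also lack the 6-month score: 0.004-0.023 SD at 10-20% missing.
- All of them lack it, 12-week score present: 0.012-0.054 SD.
- No post-operative score at all: not simulated. The model has almost nothing to work with and gains little.

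If missingness is unrelated to outcome, neither method is biased. At 20% missing the standard error is then 0.159 / 0.160 for the t-test and 0.153 / 0.149 for the model.

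**Step 4: missingness following the unseen 1-year change** (slopes 0.5 to 1). The t-test bias is 0.048-0.091 SD at 10% and 0.097-0.174 SD at 20%. The model's is 0.017-0.056 and 0.036-0.112 SD: reduced, not removed. The shift needed to correct the model is bias / fraction missing, from 0.017/0.10 = 0.17 to 0.112/0.20 = 0.56 SD.

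**Step 5: interval method.** At n = 50, uncorrected maximum-likelihood z-intervals cover about 0.936-0.948. Using t on 49 degrees of freedom gives 0.945-0.950. The model needs a stated small-sample method to hold its nominal coverage.

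**The case against.** The case for leaving the plan alone is fair. Every attrition input above is assumed. Subjects must be willing "to attend all follow-up visits" (Section 6.1), the year-1 window is ±2 months (Section 9.5), and sites may be queried for missing data (Section 11), so few scores may be lost. At 5-10% missing with the weaker slope, the bias is 0.01-0.04 SD and coverage 94-95%. Section 13 already reports the sample size with each continuous summary, so the number missing can be found by subtraction. A model helps least where the follow-up scores are missing too.

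All of this stands, and it limits how much weight the point carries. It does not remove the mismatch: the reported n shows how many subjects are absent but does not correct the estimate, and the named test cannot use scores that the schedule requires.

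A reader might infer that the primary result will be inflated in the device's favour. The documents do not support that. They do not say how many subjects will miss year 1 or which ones; if good responders stay away, the t-test understates the gain. A reader might also infer that the no-imputation sentence is itself the error or rules out a model. It does neither: a likelihood-based model imputes no individual values, so the sentence can stand.

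**Conclusion.** The point holds as a cheap improvement, not as a flaw that invalidates the study. The primary analysis is a completers' analysis labelled ITT, and it discards mandated interim scores. Under an assumed 10-20% missingness that follows the 6-month change, the mean change is off by about 0.03-0.14 SD, at most a little over four tenths of the interval half-width. At 5-10% missing with weak dependence the effect is negligible. The sign depends on who is missing. If the true gain is large, the significance test would probably be unaffected; the estimate and its interval are what change. These sizes rest wholly on the stated assumptions about attrition, correlation and dependence.

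**What to change.** In Section 13 and the SAP:

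1. Make the main 1-year analysis a likelihood-based repeated-measures model with baseline, 12-week, 6-month and 1-year KSS all as responses and unstructured covariance, fitted by REML with a small-sample degrees-of-freedom correction such as Kenward-Roger. Estimate the 1-year minus baseline mean with its 95% CI. With baseline as a response, subjects who have no post-operative score remain in the model.
2. Report the number of ITT subjects without a 1-year KSS.
3. Keep the paired t-test as a supporting analysis labelled complete-case.
4. Add a delta-shift sensitivity analysis in both directions: shift the model mean by fraction missing × delta, for example with delta from −0.75 to +0.75 SD. At 20% missing this moves the mean by up to 0.20 × 0.75 = 0.15 SD. The range covers the 0.17-0.56 SD found in Step 4.
5. State how the analysis handles scores after revision, and death, before year 1. Otherwise the model extrapolates for those subjects without saying so.

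The cost is wording and a little programming, with no new visits or data. The downsides are that the model assumes missing at random, which is why item 4 is needed; it gains little for subjects with no post-operative score; it estimates a four-visit covariance (4 × 5 / 2 = 10 parameters) from about 50 subjects; and the estimate may be slightly less favourable.

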1. INTRODUCTION, BACKGROUND & OBJECTIVE

Osteoarthritis or other degenerative changes or injury can cause damage to the structures in the knee, causing pain and discomfort, and lessening the quality of life. Knee replacement, or knee arthroplasty, is a common surgical procedure performed to relieve the pain and disability resulting from osteoarthritis. In general, the surgery consists of replacing the diseased or damaged joint surfaces of the knee with metal and plastic components shaped to allow continued motion of the knee.

Today, over 600,000 patients undergo total knee replacement each year in the United States, a number that is projected to increase greatly over the next 20 years (Kurtz). Total knee replacement has been performed since 1964 and has been shown to be an effective, long-lasting procedure with good survivorship of the implants for patients with osteoarthritis. Despite, the excellent survivorship, there are still a significant percentage of patients that remain dissatisfied with their results. Studies report 14-39% of patients report some level of dissatisfaction with their knees post-surgically (Noble et al., Bourne et al., Suda et al.).

The iTotal CR total knee replacement system and iPoly XE have been cleared by the FDA and CE marked for the treatment of osteoarthritis (OA). This study is designed to evaluate the clinical outcomes of subjects who have recently undergone surgery with the iTotal® Cruciate Retaining (CR) Total Knee Replacement System (KRS) who have also had iPoly XE Tibial Inserts implanted.

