3. STUDY DESIGN

The study is prospective and single-center. Subjects will be implanted with an iTotal® CR Knee Replacement System in conjunction with an iPoly XE insert. The study will include a minimum of 50 subjects and a maximum of 60 subjects at a single center. The study site will be located in Germany.

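### Section 13's ITT set contains only completed procedures, so a case started but not completed drops out of hospital stay, blood loss, transfusion rate and procedure length (minor; no effect if every procedure is completed)

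*Combined protocol and SAP*

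**What the plan says.** Section 13 defines two analysis sets, one after the other. For safety: "The safety population will be comprised of all subjects for whom the procedure is initiated". For efficacy: "The ITT population will be comprised of all subjects for whom the procedure is completed". It does not say what counts as completed. It makes ITT efficacy analyses primary and defines no other efficacy set.

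For the secondary list the rule is explicit: "Secondary endpoints will be analyzed for the ITT population". That list includes hospital stay, blood loss during surgery and transfusion rate. Procedure length is a secondary endpoint in Section 5.2, but Section 13 places it among the supportive efficacy endpoints ("Length of procedure: Skin to Skin"). No set is named there, so the general rule puts it on the ITT set.

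The safety analysis in Section 13 covers adverse events and serious adverse events only. Section 8 places enrolment at confirmed eligibility, before surgery.

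**The concern.** Intention-to-treat normally signals that nobody is removed because of what happened after entry. Here membership depends on the operation being finished, which is known only after enrolment and after the first incision. A reader of a peri-operative table labelled ITT could reasonably assume that it covers everyone operated on.

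The four outcomes at issue do not need a finished implantation. Blood can be lost, a transfusion given, a hospital stay accrued and operating time recorded in any case that is started. If a case is abandoned because it became complicated, leaving it out makes the summaries look better. If it is stopped early and uneventfully, leaving it out makes them look slightly worse. What is at stake is the accuracy of four descriptive results, not the primary endpoint.

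**Working it through.** The plan gives no figure to reproduce: no non-completion rate, transfusion rate, SD or power calculation. The check therefore compares the sets and then sizes the difference under stated assumptions.

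**Sets compared**

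| Set | Entry condition | Used for |
|---|---|---|
| Enrolled (Section 8) | Eligibility confirmed before surgery | No analysis |
| Safety (Section 13) | Procedure initiated | AE and SAE tables |
| Labelled ITT (Section 13) | Procedure completed | All efficacy, including the four peri-operative outcomes |

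Each set lies inside the one above it. Cases in the second but not the third are missing from the four outcomes, and no rule brings them back.

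**Inputs.** From Section 3: N = 50 to 60. Assumed: k non-completed cases, a non-completion risk p, t transfusions among completers, and a distance d (in SDs) between non-completed and completed cases.

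**Chance that it arises**, 1 - (1 - p)^N:

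| p (assumed) | N = 50 | N = 60 |
|---|---|---|
| 0.1% | 4.9% | 5.8% |
| 0.5% | 22.2% | 26.0% |
| 1% | 39.5% | 45.3% |
| 2% | 63.6% | 70.2% |

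**Transfusion rate.** The plan reports t/(N - k). All initiated procedures give between t/N (no excluded case transfused) and (t + k)/N (all transfused). For N = 50, k = 1:

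| t | Plan, exact 95% CI | All initiated, case transfused | All initiated, case not transfused |
|---|---|---|---|
| 0 | 0/49 = 0.0% (0 to 7.3) | 1/50 = 2.0% (+2.0 points) | 0/50 = 0.0% (0) |
| 2 | 2/49 = 4.1% (0.5 to 14.0) | 3/50 = 6.0% (+1.9) | 2/50 = 4.0% (-0.1) |
| 5 | 5/49 = 10.2% (3.4 to 22.2) | 6/50 = 12.0% (+1.8) | 5/50 = 10.0% (-0.2) |

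Each shifted value lies inside the interval the plan would report. At N = 60 with t = 2, the plan gives 2/59 = 3.4%, against 3/60 = 5.0% or 2/60 = 3.3%. With three such cases at N = 50 and t = 5, it gives 5/47 = 10.6%, against 10.0% to 16.0%.

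**Means (stay, blood loss, procedure length).** Shift = (k/N) x d. With d = ±3:

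- N = 50: k = 1 gives 3/50 = ±0.06 SD; k = 2 gives 6/50 = ±0.12 SD.
- N = 60: k = 1 gives 3/60 = ±0.05 SD; k = 2 gives 6/60 = ±0.10 SD.

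The 95% CI half-width for completers is t-quantile/√n: 0.287 SD for n = 49, 0.290 for n = 48, 0.261 for n = 59 and 0.263 for n = 58. The 3 SD limit is an assumption, and a case further out shifts the mean more. For one case at N = 50 to move the mean by the whole half-width, d would have to be about 0.287 x 50 = 14.4 SD.

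If k = 0, the initiated and completed sets coincide and every difference is zero.

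**The case against.** The strongest reply is that nothing is concealed. The definition is stated openly beside the safety definition, and a single-arm study has no randomised comparison for intention-to-treat to protect. That stands, and it limits the label problem to a correction of terminology.

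Restricting device outcomes to implanted subjects is also sound. The aim in Section 1 concerns people "who have also had iPoly XE Tibial Inserts implanted", and Section 3 says: "Subjects will be implanted with an iTotal® CR Knee Replacement System in conjunction with an iPoly XE insert". Section 5.1 times the main outcome from implantation: "The study primary endpoint is pain and function at 1 Year after implantation, as measured by". A reader might infer that the primary analysis is biased, or that all endpoints belong on everyone enrolled. The documents do not support either. Without the implant there is no post-implant score to include, and the fact that enrolment precedes surgery justifies only the new name and the subject flow.

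It can be said that the safety population already covers these cases. It does so in part. Serious events are recorded whatever their relation to the device, so a seriously complicated case stays visible. Its blood loss, transfusion, stay and operating time do not enter the summaries, however, and Section 10 collects non-serious events only if at least possibly device-related. Nor does the reference in Section 13 to a later analysis plan resolve the point, since it defers only the details of testing.

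Finally, blood loss and operating time from an abandoned case may describe a partial operation, so pooling them with full operations is imperfect. That is fair. It argues for showing both sets and listing the cases, and for treating blood loss and procedure length alike.

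**Conclusion.** The point holds and is minor. The label is wrong as written, and cases started but not completed are excluded by rule from four outcomes they could contribute to.

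The stronger inference, that the plan makes its peri-operative results look better, is not supported. The direction depends on what happens in cases that may never occur, and the documents give no indication of how often to expect them. The working shows changes well inside the sampling uncertainty for one case. Several such cases would matter more: with three in 50, the transfusion rate could differ by up to 5.4 points. All of this rests on assumed non-completion and transfusion rates and, for the means, on the 3 SD limit. There is no performance threshold, so no conclusion of success or failure turns on it.

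The undefined term adds some uncertainty. If completed means that the operation was finished with any implant, only abandoned operations are excluded. If it means that the study device was implanted, conversions to another implant are excluded as well. Section 13 allows both readings.

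**What to change.** 1. Rename the set the completed-procedure population, and state whether a case finished with another implant belongs to it.
2. Report hospital stay, blood loss, transfusion rate and procedure length on all initiated procedures (the existing safety population) side by side with the completed-procedure set. List each non-completed case individually, because its blood loss and operating time may reflect a partial operation.
3. Keep KSS, KOOS, revision, limb alignment and radiographic endpoints on the completed-procedure set under its correct name.
4. Report the numbers enrolled, initiated and completed, with reasons for non-completion.
5. Confirm that the Surgical and Discharge Summary forms are filled in for every initiated case. Section 9.2 does not make them conditional on completion, but it describes a visit at which the device is implanted, and the early-termination list in Section 9.8 names neither form. One sentence would settle it.

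The cost is a few sentences in Section 13, one flow table and slightly more reporting. No subjects or visits are added. The peri-operative figures may become slightly less favourable.
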